# 4.7 Record keeping procedures for trial products

The trial sites will be provided with the drugs (the study drug and comparator drug) in the amounts enough for the trial completion, taking into account the planned number of patients to be screened. An authorized trial site specialist shall keep a logbook for the drugs where the drugs receipt to the trial site, dispensing to the subjects, and return of the unused drugs are noted. Storage conditions must be also noted. The study drugs may be used for the purposes of this clinical trial only.

Authorized representatives of the Sponsor or regulatory authorities may check the drugs logbook or availability of the drugs at stock during the trial site audit/monitoring. The drugs must be stored under the required conditions in a room with an access for the authorized personnel responsible for the drugs dispensing only.

#### 4.8 Storing and unblinding of randomization codes

This is an open trial. The Sponsor will keep a list of the randomization codes. The trial sites will be provided with the sealed envelopes containing randomization numbers. The envelopes must be opened

# Confidential

Page 59 of 104 Version 1.0 of September 28, 2016

Protocol No. TE 004 ANG LOZ

sequentially, from the smaller numbers to bigger ones, to avoid a breach of a randomization principle.

# 4.9 A list of all the data to be recorded in eCRF

All the data obtained during this clinical trial will be considered to be primary data and subject to record in eCRF.

#### 5 Selection and exclusion of the subjects

#### 5.1 Inclusion criteria

The patients who meet all the inclusion criteria listed below will be included in the trial:

- 1. The Informed Consent Form voluntarily signed by the patient.
- 2. Men and women at the age of 18 to 45 years old, inclusively.
- 3. A diagnosis of acute, uncomplicated, inflammatory and infectious condition of the pharynx associated with the inflammation and pain in the throat.
- 4. Manifestation of the first signs of acute, uncomplicated, inflammatory and infectious condition of the throat (pharyngitis and/or tonsillitis) not more than 48 hours before the inclusion.
- 5. A baseline total sum of TSS (Tonsillopharyngitis Severity Score) points  $\geq$ 5.
- 6. Body temperature measured in the axillary cavity is less than 37.5 °C.
- 7. Women with childbearing potential should demonstrate a negative pregnancy test result at screening (except for the women after surgical sterilization or menopause for more than 2 years) and use the established contraception methods for at least 3 months before the initiation of the trial therapy and 1 month after completion of the trial.
- 8. Men should use adequate contraception during the trial, since signing of the Informed Consent Form and till the trial completion, and for 30 days after the trial completion.
- 9. Ability to understand the presented information on the clinical trial, readiness to comply with the protocol, ability to use the study drugs by oneself and evaluate the symptoms according to VAS (visual analogue scale) or other questionnaires according to the protocol.

#### 5.2 Non-inclusion criteria

The patients who comply with at least one of the criteria listed below will not be included:

- 1. Prior tonsillectomy, tonsillotomy.
- 2. Chronic conditions of the nasopharynx or oropharynx, ulcerative oral disorders.
- 3. History of hypersensitivity or allergic reactions to any components of the study drugs or local anesthetics.
- 4. Use of analgesics during less than 12 hours before the trial start and/or impossibility to discontinue the analgesics for the trial period.

- 5. Use of antibiotics during less than 48 hours before the trial start and/or planned use of antibiotics during the trial.
- 6. Use of topical drugs (aerosols, gargle solutions, fast-disintegrating tablets/lozenges/pastilles) in the pharynx during less than 12 hours before the trial start and/or impossibility to discontinue topical drugs, except for the study drugs, for the trial period.
- 7. Use of the systemic, inhalation, or nasal glucocorticosteroids during 30 days before the trial start and/or planned use of the glucocorticosteroids (except for the topical skin drugs) during the trial.
- 8. Impossibility to discontinue other drugs which might influence the trial results, e.g. antiviral or prohibited concomitant drugs (see *Prohibited concomitant therapy* section), for the trial period.
- 9. Signs of a primary bacterial pharyngitis or secondary bacterial infection (including body temperature increase above 37.5 °C, purulent pharyngeal pellicles, significant intoxication, leukocytosis, neutrocytosis, WBC differential's shift to the left (increase in stab neutrophils, presence of younger neutrophils), ESR more than 30 mm/h).
- 10. Granular pharyngitis.
- 11. Signs of rhinitis, sinusitis, otitis, eustachitis, laryngitis, tracheitis, bronchitis (such conditions require therapy which might influence the trial results).
- 12. Phenylketonuria.
- 13. Deficit of saccharase or isomaltase (according to anamnesis data).
- 14. Glucose-galactose malabsorption (according to anamnesis data).
- 15. Fructose intolerance.
- 16. Diabetes mellitus.
- 17. Glucose-6-phosphate dehydrogenase deficiency (according to anamnesis data).
- 18. Hemochromatosis.
- 19. Anemia (Hb less than 120 g/l according to hematology test).
- 20. Hyperoxaluria.
- 21. Urolithiasis.
- 22. Myasthenia.
- 23. Severe, uncontrolled, cardiovascular condition which, in the Investigator's opinion, preclude the patient from participation in the trial, namely:
  - a. Severe (IV acc. to Canadian Cardiovascular Society) or unstable angina;
  - b. Decompensated chronic heart failure (NYHA stage IV);
  - c. Myocardial infarction for the last 6 months;
  - d. uncontrolled arterial hypertension (BP more than 180/115 mm Hg).

- 24. Pregnant and/or breastfeeding women.
- 25. Participation in other clinical trials at the screening visit or for 30 days before the screening visit.
- 26. Surgical intervention for 30 days before the screening visit or planned surgical treatment during the trial (sooner than a follow-up visit is completed), including diagnostic procedures or hospital stay.
- 27. Known or suspected narcotic/alcohol abuse.
- 28. A suspected low compliance or incapability of the patient to perform the procedures and comply with restrictions according to the trial protocol (e.g., due to mental disorders).
- 29. Any cardiovascular, renal, hepatic, gastrointestinal, endocrine, or nervous disorders, or any other conditions/diseases which, in the Investigator's opinion, might inflict harm to the patient's health.

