	• AEs and/or SAEs rates per trial arms;						
	• Global tolerance evaluation during the trial by the Investigator and patient;						
	• Vital signs (heart rate, blood pressure, body temperature, breathing rate);						
	• ECG parameters;						
	Laboratory results.						
	The AEs will be described according to the scheme given below:						
	• ae description;						
	• ae severity;						
	• ae duration;						
	• Relation to the study drug;						
	• Outcome.						
	All AEs will be coded according to MedDRA terms.						
Inclusion criteria	The patients who meet all the inclusion criteria listed below will be included in the trial:						
	1. The Informed Consent Form voluntarily signed by the patient.						
	2. Men and women at the age of 18 to 45 years old, inclusively.						
	3. Diagnosis of acute, uncomplicated, inflammatory and infectious condition of the pharynx associated with the inflammation and pain in the throat.						
	4. Manifestation of the first signs of acute, uncomplicated, inflammatory and infectious condition of the throat (pharyngitis and/or tonsillitis) not more than 48 hours before the inclusion.						

	5	A baseline total sum of TSS (Tonsillopharyngitis Severity Score) points $\geq 5$ .					
	6	Body temperature measured in the axillary cavity is less than 37.5 °C.					
	7	Women with childbearing potential should demonstrate a negative pregnancy test result at screening (except for the women after surgical sterilization or menopause for more than 2 years) and use the established contraception methods for at least 3 months before the initiation of the trial therapy and 1 month after completion of the trial.					
	8	Men should use adequate contraception during the trial, since signing of th Informed Consent Form and till the trial completion, and for 30 days after th trial completion.					
	9	Ability to understand the presented information on the clinical trial, readiness to comply with the protocol, ability to use the study drugs by oneself and evaluate the symptoms according to VAS (visual analogue scale) or other questionnaires according to the protocol.					
Non-inclusion criteria	The pa	tients who comply with at least one of the criteria listed below will not be					
	include	d:					
	1.	Prior tonsillectomy, tonsillotomy.					
	2.	Chronic conditions of the nasopharynx or oropharynx, ulcerative oral disorders.					
	3.	A history of hypersensitivity or allergic reactions to any components of the study drugs or local anesthetics.					

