# 2.1 Names and description of study products

#### 2.1.1 Study drug

#### Angal, lozenges [menthol], 1 mg + 5 mg.

Qualitative and quantitative composition

One lozenge contains chlorhexidini dihydrochloridum 5 mg and lidocaini hydrochloridum 1 mg.

*Excipients*: levomenthol 5 mg, anhydrous citric acid 5.5 mg, magnesium stearate 25 mg, sorbitol 1,208.5 mg.

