# **Contraindications**

- Hypersensitivity to the active substances (chlorhexidine or lidocaine), amide-type local anesthetics or to any of the excipients.
- Children under 5 years of age.
- Children with a history of muscle spasms (including fever-induced spasms), as Angal contains levomenthol.

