#### **Composition and presentation**

Lozenges	1 lozenge
chlorhexidine diacetate	2 mg
tetracaine hydrochloride	0.20 mg
ascorbic acid	50 mg
Excipients: dextrose syrup 945.00 mg, saccharose 1,435.00 mg, natural oil flavoring 4.00 mg, mint flavoring 0.30 mg, red carmine colorant E120 0.10 mg, purified water 63.40 mg.	

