#### Contraindications

Hypersensitivity to the components of the drug, pediatric age below 5 years old, I pregnancy trimester, sucrase-isomaltase deficiency, fructose intolerance, glucose-galactose malabsorption, hypersensitivity to other topical anesthetics of the esters group or paraaminobenzoic acid or its derivatives.

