# 4.2.4 Trial stages

# 4.2.4.1 Screening/randomization/therapy initiation (Visit 1)

Visit 1 is scheduled for Day 1. At this visit, the doctor evaluates the patient's eligibility for the trial. If no non-inclusion criteria are met, the patient undergoes randomization, is given the study drug/comparator drug and a patient's diary, and is instructed on the patient's diary completion requirements. Screening visit procedures:

- Signing of the Informed Consent Form;
- Demographic data (date of birth, sex, age);
- Measurement of weight and height;
- Anamnesis gathering;
- Records on the concomitant therapy;
- Evaluation of inclusion/non-inclusion criteria;
- Evaluation of the throat pain intensity according to VAS;
- Fill-in of TSS questionnaire by the Investigator;
- Physical examination (including oropharynx);
- Measurement of the main vital signs;
- Hematology;
- Biochemistry;
- Urine pregnancy test;
- 12-lead ECG;
- Evaluation of inclusion/non-inclusion criteria;
- Randomization;
- Dispensing of the study drugs;
- Provision with the patient's diaries and training on the fill-in rules;
- Initiation of therapy with the study drugs;
- Evaluation of adverse events (including based on results of the throat and pharynx examination).

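### Non-inclusion criterion 3 leaves out part of the comparator's contraindications: hypersensitivity to para-aminobenzoic acid or to its derivatives that are not local anesthetics

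*Protocol*

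**What the plan says.** Protocol section 5.2, non-inclusion criterion 3, bars patients with "History of hypersensitivity or allergic reactions to any components of the study drugs or local anesthetics". The synopsis has the same rule: "A history of hypersensitivity or allergic reactions to any components of the study drugs or local anesthetics".

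The comparator's contraindications, set out in section 2.1.2, end with "hypersensitivity to other topical anesthetics of the esters group or paraaminobenzoic acid or its derivatives". The corresponding list for Angal in section 2.1.1 covers "Hypersensitivity to the active substances (chlorhexidine or lidocaine), amide-type local anesthetics or to any of the excipients" and does not mention PABA.

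The last non-inclusion criterion, No. 29, is a general clause. It reaches "any other conditions/diseases which, in the Investigator's opinion, might inflict harm to the patient's health".

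Section 4.2.4.1 describes what follows the eligibility check at Visit 1: "If no non-inclusion criteria are met, the patient undergoes randomization, is given the study drug/comparator drug".

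**The concern.** A patient in a 1:1 randomised trial should be able to take either drug before the envelope is opened. A patient with a recorded PABA allergy is contraindicated for the comparator under section 2.1.2, yet breaches no named entry criterion. Whether that patient is randomised depends on the individual investigator.

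This looks like an omission rather than a choice. The entry criteria otherwise follow the comparator's label closely. They also make mandatory exclusions of several conditions that the label lists only as precautions: diabetes (No. 16), glucose-6-phosphate dehydrogenase deficiency (No. 17), hemochromatosis (No. 18), hyperoxaluria (No. 20) and urolithiasis (No. 21). So a stated contraindication is left to judgment while lesser precautions are not, and the protocol gives no reason.

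What is at stake is a possible contraindicated dose in a very small number of patients. No inference from the trial depends on it.

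**Working it through.** No formula applies. The check sets each comparator contraindication in section 2.1.2 against the entry rules in sections 5.1 and 5.2.

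| Comparator contraindication (2.1.2) | Entry rule | Match |
|---|---|---|
| 1. Hypersensitivity to its components | Non-inclusion 3 | Full |
| 2. Age below 5 years | Inclusion 2 (18 to 45 years) | Full |
| 3. First-trimester pregnancy | Non-inclusion 24 | Full |
| 4. Sucrase-isomaltase deficiency | Non-inclusion 13 | Full |
| 5. Fructose intolerance | Non-inclusion 15 | Full |
| 6. Glucose-galactose malabsorption | Non-inclusion 14 | Full |
| 7. Ester anesthetics, or PABA or its derivatives | Non-inclusion 3, for the anesthetics only | Partial |

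That gives 7 entries, of which 6 are fully matched and 1 is partly matched.

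Could criterion 3 be read to reach PABA through entry 7? It has two limbs.

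- **Components of the study drugs.** Section 8.3.3 counts the control drug as a study drug, so this limb can be read to include the comparator's ingredients. Those are chlorhexidine diacetate, tetracaine hydrochloride and ascorbic acid, with excipients "dextrose syrup 945.00 mg, saccharose 1,435.00 mg, natural oil flavoring 4.00 mg, mint flavoring 0.30 mg, red carmine colorant E120 0.10 mg" and purified water. Angal contains chlorhexidine dihydrochloride and lidocaine hydrochloride, with "levomenthol 5 mg, anhydrous citric acid 5.5 mg, magnesium stearate 25 mg, sorbitol 1,208.5 mg". PABA is in neither list, so this limb does not reach it.
- **Local anesthetics.** This covers the ester anesthetics, including any PABA derivative that is itself a local anesthetic. It does not cover PABA or the remaining derivatives.

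No other criterion in section 5.1, section 5.2 or the synopsis names PABA. Section 4.2.3.2.1 does require an allergy history at Visit 1, but no rule links a PABA allergy to a decision. That leaves No. 29.

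With 1:1 allocation, a patient not stopped under No. 29 has probability 1/(1+1) = 0.5 of being assigned to the comparator. Assignment is not exposure, because further checks stand before the first dose. The documents give no prevalence of PABA allergy, so no expected number is calculated.

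**The case against.** The strongest reply is that the patient is already protected. Section 2.4 says both drugs are prescribed according to their Prescribing Information, section 4.4.4 repeats this for the comparator, and the contraindication is printed in the protocol itself. An investigator who records a PABA allergy therefore knows, before opening the envelope, that one of the two possible assignments should not be given. No. 29 is itself a non-inclusion rule, and with a documented allergy listed as a contraindication the judgment it asks for is easy. The trial is open (section 4.3.2), and the investigator can withdraw a patient (section 5.3.1, items 3 and 12). All these layers would have to fail together for one contraindicated dose. A protocol may also rely on a general harm clause plus the label instead of repeating every label term.

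Much of this stands as a statement about risk: exposure is unlikely, and no practical harm has been shown. It does not close the gap in the criteria.

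- The Prescribing Information statements concern prescribing and regimen; they are not entry criteria. The protocol restates the comparator's other contraindications as criteria, so it does not rely on that reference alone.
- No. 29 still depends on opinion, and investigators may differ. A patient enrolled despite the allergy breaches no named criterion, so removal for false inclusion or for meeting a non-inclusion criterion (section 5.3.1, items 9 and 10) is not clearly triggered.
- Knowledge of the arm comes only after randomisation. Randomisation, dispensing and the start of therapy all take place at Visit 1, so the time to catch the problem is short. A patient stopped then is not replaced (section 5.3.3). This last point is small: a patient who never takes a dose is outside the ITT and safety populations (section 9.7), and the sample size allows for 10% discontinuation.

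**Conclusion.** The concern holds as a minor patient-safety wording point. One part of one of the comparator's seven contraindication entries is not a mandatory exclusion, and the only entry criterion that can apply before randomisation is discretionary. Confidence is high on the mismatch in wording. Nothing is claimed about how many patients it touches or what would happen to them, since the documents give neither a prevalence nor a clinical consequence. The number is probably very small. Alpha, power, the non-inferiority margin and the primary analysis are untouched.

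The conclusion rests on two readings: that the composition lists in sections 2.1.1 and 2.1.2 are complete for this purpose, and that the references to Prescribing Information in sections 2.4 and 4.4.4 do not act as entry criteria.

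**What to change.** Extend non-inclusion criterion 3, in section 5.2 and in the synopsis, so that after the study-drug components and local anesthetics it also names para-aminobenzoic acid or its derivatives. Apply it through the allergy history already collected at Visit 1 under section 4.2.3.2.1.

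The cost is one phrase in two places, with no extra test or visit. A very small number of additional patients would be excluded, including some for whom Angal itself is not contraindicated. The protocol already accepts that trade: section 2.1.1 says diabetic patients can use Angal, yet criterion 16 excludes them.

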# 5.3 Exclusion criteria

#### 5.3.1 Terms and conditions for the subjects' exclusion from the trial

The subjects may be excluded from the trial on their own free will at any moment, without giving any reason, as well as upon decision of the Investigator or Sponsor in cases when continuation of the participation may inflict harm to the patient's health and/or life. In addition, the patient must be excluded in the cases listed below:

- 1. Negative course of the disease with signs of the secondary bacterial infection (including body temperature increase above 37.5 °C).
- 2. The Ethics Committee, regulatory authorities, or Sponsor terminate the trial or participation of the specific trial site for any reason.
- 3. The Investigator's decision to withdraw the patient from the trial in the interests of the patient.
- 4. Withdrawal of the informed consent (unwillingness of the patient to continue his/her participation in the trial).
- 5. Serious deviation from the trial protocol.
- 6. Individual intolerance of the study drugs.
- 7. Clinically significant adverse event or serious adverse event.
- 8. Patient's non-compliance.
- 9. False inclusion (e.g., the patient was included in breach of the inclusion/non-inclusion criteria).
- 10. The patient complies with the non-inclusion criteria during the trial.
- 11. The patient receives or requires an additional therapy which might influence the trial results or patient's safety (see *Prohibited concomitant therapy* section).

12. Other conditions or events which, in the Investigator's opinion, require the patient's exclusion from the trial.

#### 5.3.1.1 Terms and volume of data on the excluded subjects

In case of trial discontinuation on the subject's free will, the Investigator should make effort to find out the reason thereof. In case of trial discontinuation due to AEs/SAEs, the subject should be followed-up until the AEs/SAEs are resolved. In case of discontinuation from the trial prematurely, the patient should visit the trial site for early discontinuation procedures (as an unscheduled visit); if the patient refuses to visit the trial site, he/she should be contacted by phone with recording of all available information.

# 5.3.2 Terms and conditions of suspend or discontinuation of the trial therapy

The patients may stop taking the study drugs according to the protocol or upon withdrawal from the trial.

#### 5.3.3 Replacement of the excluded subjects

Replacement of the excluded patients during the trial is not envisaged.

#### 5.4 Acceptable contraception methods

The patients must follow adequate contraceptive methods throughout the trial as well as within 30 days after its completion.

Effective contraception methods include:

- True abstinence;
- Oral contraceptives (combination drugs containing progestogen, or progestogen alone);
- Injectable progestogen;
- Levonorgestrel implants;
- Estrogen-containing vaginal ring;
- Transdermal contraceptive patches;
- Intrauterine device (IUD) or intrauterine system (IUS) meeting the efficacy criteria according to Prescribing Information;
- A male partner has been sterile (vasectomy with documented azoospermia) prior to inclusion of a woman, provided that he is the only partner of the female patient. For the purpose of this definition, "documented" is related to the result of a patient's medical examination by the Investigator/responsible person or a patient's past medical history review for evaluation of eligibility for

inclusion, obtained during the interview with a patient or from his/her medical records.

• Double barrier method: a condom or an occlusive cap (diaphragm or cervical/vault caps) with a spermicide (foam/gel/film/cream/suppository).

Men should use adequate contraception during the trial, since signing of the Informed Consent Form and till the trial completion, and for 30 days after the trial completion.

# 6 Trial therapy

# 6.1 Therapy regimens

The study drug group (Angal, lozenges [menthol]): 1 lozenge, as needed, up to 6–10 times per day, for 4 days or until full recovery (total  $TSS \le 2$ ) (whichever occurs first during 4 days of therapy). A single dose of Angal is 1 lozenge. The lozenges are intended for full dissolution in the oral cavity. One lozenge is slowly disintegrating in the mouth.

The comparator drug group (ANTI-ANGIN® FORMULA, lozenges): 1 lozenge with a not less than 2hour interval, up to 6 lozenges per day, for 5 days or until full recovery (total TSS  $\leq$  2) (whichever occurs first during 5 days of therapy). One dose of ANTI-ANGIN® FORMULA is 1 lozenge (keep in the mouth till full dissolution). The lozenges are intended for full dissolution in the oral cavity. One lozenge is slowly disintegrating in the mouth.

